Accuracy of Ultra-Low-Dose CT (ULDCT) of the Chest Compared to Plain Film in an Unfiltered Emergency Patient Cohort

Study protocol and statistical analysis plan

English Version

Version 1.3
24th of April 2019

Table of contents

1	AUTHORS	3
2	PARTICIPANTS	3
3	PROJECT TITLE	4
4	BACKGROUND AND SUMMARY	5
5	STUDY DESIGN.....	7
6	HYPOTHESES AND OUTCOME MEASURES	10
7	INCLUSION CRITERIA	11
8	EXCLUSION CRITERIA	12
9	ETHICAL CONSIDERATIONS	12
10	RECRUITMENT	13
11	STUDY DURATION	13
12	RADIATION DOSE.....	13
13	RADIOLOGICAL ANALYSIS	14
14	STATISTICAL ANALYSIS PLAN	15
15	COMPENSATION	15
16	STUDY SUSPENSION	16
17	DATA MANAGEMENT AND DATA PROTECTION	16
18	FUNDING.....	16

ULDCT project

1 Authors

- Univ.[name].-Doz. Dr.med.univ. [name], MBA
- Mag.rer.soc.oec. Dr.med.univ. [name]
- Mag. [name]
- ao.Univ.-[name].-Ing. [name]
- Ass.-[name].-Doz. Dr.med.univ. [name], MBA
- Assoc.[name].-Doz. Dr.med.univ. [name]
- Dr.med.univ. [name]
- Assoc.[name].-Doz. Dr.med.univ. [name]
- Assoc.[name].-Doz. Dr.med.univ. [name]
- Assoc.[name].-Doz. Dr.med.univ. [name]
- Dr.med.univ. [name]
- o.Univ.-[name].med.univ. [name]
- ao.Univ.-[name].med.univ. [name]
- Ass.-[name].med.univ. [name]
- Dr.med.univ. [name]
- Dr.med.univ. [name]

2 Participants

Intended number of participants	250
Limiting age, minimum	18 years
Limiting age, maximum	92 years
Ability to provide informed consent	Yes
Male participants	Yes

Female participants	Yes
Duration of participation in the trial for each participant	Approximately two hours for each patient from inclusion in the study until the therapeutic consequences are established.
Active phase	Six months
Follow-ups	Within the trial no follow-up is intended. However, if clinically indicated follow-ups are performed, this data may be used in the analysis phase of the study for final diagnosis.
Estimated duration of the trial	One year (six months of acquisition, six months of evaluation)

3 Project title

Brief title

Accuracy of Ultra-Low-Dose-CT of the Chest Compared to Plain Film in an Unfiltered Emergency Department Patient Cohort

Acronym

UP-Chest

Official title

Accuracy of Ultra-low-dose-CT (ULDCT) of the Chest Compared to Plain Film in an Unfiltered Emergency Department Patient Cohort

4 Background and summary

For nearly a century, chest X-ray (plain film, projectional radiography) has been the established primary imaging modality for patients with acute chest pain, suspected pneumonia, and / or acute dyspnoea in the diagnostic pathway of emergency departments, although the sensitivity and specificity of this X-ray technique are moderate. (Long et al. 2017; Andronikou et al. 2017; Chalmers 2016; Martindale et al. 2016; Cardinale et al. 2014; Chawla et al. 2016)

The widespread availability and use of chest X-ray is due to the low acquisition and operating costs for projectional radiography equipment, the short examination time, and the very low radiation exposure. In addition, projectional radiography of the chest often serves as a guide for further, more sensitive, diagnostical procedures. However, these advantages are partially offset by the disadvantages inherent to projectional methods: anatomical structures may superpose or mask pathological structures. As a result, some areas of the lung may be obscured, and assessment may therefore be limited.

Whereas computed tomography was reserved for certain clinical questions over the last few decades, and, in most cases, served as a second imaging approach after plain film radiography, it has increasingly evolved as a primary imaging modality for several indications (e.g., suspicion of pulmonary embolism, highly suspected aortic dissection). This rise of computed tomography was due not only to its significant advantage of no superposition, but also partly driven by the marked reduction in radiation dose needed without sacrificing image quality. This was driven by the development of new detectors, modulation of tube current and voltage, as well as iterative reconstruction techniques. As a result, recent computed tomography scanners currently offer not only a more precise visualization of differences in tissue-attenuation and the significant advantage of the absence of artefacts due to superposition, but also allow for imaging with a considerably reduced radiation dosage compared to older scanners. (Zinsser et al. 2018; Anon 2014; Brenner and Hall 2007; Berrington de González et al. 2009) (O’Hora and Foley 2018; Moser et al. 2017; Kubo et al. 2014; Kubo et al. 2017) Therefore, computed tomography may now be utilized as screening method in specific indications that carry an increased risk of certain pathologies (e.g., in long-time smokers) (Horeweg et al. 2014; Walter et al. 2016; Yousaf-Khan,

van der Aalst, de Jong, Heuvelmans, Scholten, Lammers, et al. 2017; Yousaf-Khan, van der Aalst, de Jong, Heuvelmans, Scholten, Walter, et al. 2017; National Lung Screening Trial Research Team et al. 2011; van der Aalst et al. 2016; Ruchalski and Brown 2016; Fintelmann et al. 2017). The introduction of the latest generation of computed tomography devices about three years ago allowed for an even further reduction in dose by filtering out low-energy photons using a tin filter, which offers the possibility of a reduction in radiation dose by another 50 % or more for established CT indications. For specific indications (e.g., lung nodules in follow-up), the radiation dose may even be reduced to a tenth or one-hundredth of a standard-dose CT (SDCT). (Braun et al. 2015; Suntharalingam et al. 2018; Haubenreisser et al. 2015)

The current reference dose-length-product (DLP) in Germany for thoracic standard-dose CT (SDCT) is ~350 mGycm (effective dose ~6 mSv) and, for thoracic low-dose-CT (LDCT / HR-CT), ~100 mGycm (effective dose ~1.7 mSv) (Schegerer 2016). However, the latest devices (third-generation dual-energy CT) provide the opportunity to considerably reduce the reference dose of thoracic low-dose CT. In the current literature, these scans are referred to as Ultra-Low-Dose-CT (ULDCT) and are usually associated with a radiation dosage of 0.14 to 0.5 mSv. For this dose range, no standardized reference values have been published as yet. (Macri et al. 2016; Messerli, Ottilinger, et al. 2017; Messerli, Giannopoulos, et al. 2017; Messerli, Hechelhammer, et al. 2017; Vardhanabhuti et al. 2017; Martini et al. 2016; Rob et al. 2017; Moore et al. 2015; Braun et al. 2015)

The limiting factors of ULDCT are quantum noise, loss of spatial resolution, and other image artefacts (Kim et al. 2015). Therefore, careful selection of appropriate CT protocols and dosage is mandatory in order to achieve sufficient image quality to answer the respective diagnostic question.

Several papers have been published on the subject of ULDCT, which are dedicated to the comparison of ULDCT with LDCT and/or SDCT. These papers conclude that this technology may be used with sufficient sensitivity and specificity for indications such as dyspnea, emphysema, or lung nodules. (Macri et al. 2016; Messerli, Ottilinger, et al. 2017; Messerli, Giannopoulos, et al. 2017; Messerli, Hechelhammer, et al. 2017; Vardhanabhuti et al. 2017;

Martini et al. 2016; Rob et al. 2017; Moore et al. 2015) Due to the potential to reduce the radiation dose to less than 1/30 of a standard-dose CT while still providing acceptable image quality with the latest generation of devices, ULDCT of the chest is emerging as an interesting alternative to conventional chest X-ray.

To the best of the authors' knowledge, there are currently no studies comparing and evaluating ultra-low-dose-CT as a primary imaging alternative to chest X-ray in emergency department patients.

[figure not shown]
[figure not shown]
This study aims to compare ULDCT and plain film of the chest with regard to their accuracy in an unfiltered patient cohort of an emergency department. For this purpose, our ULDCT protocol will use the lowest possible dose at which image quality is diagnostically sufficient (approximately 0.2 mSv effective dose). This corresponds to less than 1/30 of the radiation dose of a standard-dose CT of the chest and to only about 2.5 times the dose of a chest X-ray in two views. This dose is equal to less than a month of natural background radiation in Austria and less than the radiation exposure on an intercontinental flight. (Bundesministerium für Arbeit, Soziales, Gesundheit und Konsumentenschutz 2018b; Bundesministerium für Arbeit, Soziales, Gesundheit und Konsumentenschutz 2018a; Ditto et al. 2013)

[figure not shown]
In addition to the accuracy of ULDCT of the chest compared to plain film of the chest, this trial also aims to analyze the clinical relevance of both methods by assessing the respective impact on final diagnosis, as well as possible changes in therapy.

5 Study Design

Study Type	Interventional
Primary Purpose	Diagnostic
Number of Arms	2
Masking (prospective)	None (open label)
Allocation	Randomized
Enrolment	250

Arms	Assigned Interventions

Reporting-order: Plain Film - ULDC
 
The plain film of half the participants (randomized) will be submitted for reporting by a radiologist as a first imaging method. After finishing this report, the same radiologist will assess the ULDC of this participant. In this second report, the findings of both examinations will be summarized, and a second report will be filed.
 
Emergency physicians will first receive the report for the plain film of the chest and will be asked for the diagnosis and its probability. Next, the report for ULDC will be presented to them. Again, diagnosis and probabilities will be documented.
	
Diagnostic Test: ULDC
 
Ultra-Low-Dose-CT (ULDC) of the chest using tin filters with third-generation dual-energy CT devices. The projected dose used will be approximately 0.2 mSv per ULDC of the chest.

Reporting-order: ULDC - Plain Film
 
For half the participants (randomized) radiologists will first receive the data from ULDC of the chest and write a report. Subsequently, they will receive the data from the plain film of the chest and may expand their report (explicitly separated).
 
Emergency physicians will first receive the report for the ULDC of the chest and will be asked for probabilities of the nine most frequent diagnoses in chest-imaging plus "other". Next, they will be presented with the report for the plain film and will again be asked to give an estimation of the probabilities for the same diagnoses as before.
	
Diagnostic Test: ULDC
 
Ultra-Low-Dose-CT (ULDC) of the chest using tin filters with third-generation dual-energy CT devices. The projected dose used will be approximately 0.2 mSv per ULDC of the chest.

6 Hypotheses and outcome measures

Null hypothesis:

- There is no difference in accuracy between ULDCCT of the thorax and plain film of the thorax regarding the primary diagnosis.

Alternative hypothesis:

- ULDCCT of the thorax offers higher accuracy than plain film of the thorax regarding the primary diagnosis.

Primary Outcome Measure:

Accuracy of ultra-low-dose-CT of the chest and plain film of the chest

Description:

Initial radiologic diagnostic accuracy of both methods will be assessed by analyzing the number of reports that are changed after the images of the second modality become available to the radiologist in Arm 1 compared to Arm 2.

In a final approach, the diagnostic accuracy will be analyzed by retrospectively comparing all reports with the gold standard, which will be built from all available patient data at the end of the study, including all follow-up imaging studies and laboratory tests.

Secondary Outcome Measures:

- Sensitivity and specificity in ULDCT and plain film
- Frequency of change in radiological diagnosis
- Frequency of change in emergency physician's diagnosis
- Frequency of change in (planned) therapeutic course of action by emergency physician
- Frequency of accidental diagnosis in ULDCT of the chest and plain film of the chest
- Frequency of additional diagnostic imaging needed
- Frequency of unclear reports in ULDCT and plain film
- Diagnostic confidence in ULDCT and plain film by radiologist
- Diagnostic confidence in ULDCT and plain film by emergency physician

7 Inclusion criteria

Sex	All
Gender-based	No
Age limits	Minimum: 18 years Maximum: 92 years
Accept healthy volunteers	No
Participants	All patients who are assigned to a clinically indicated chest X-ray by the emergency department of Vienna General Hospital
Consent	Ability to provide informed consent Informed consent after detailed patient briefing

8 Exclusion criteria

Clinical status	A critical clinical condition that does not allow the examination with both modalities (ULDCT of the chest, chest X-ray)
Assignment	Assigned to chest X-ray as follow-up
Pregnancy	Women with positive β -HCG-test

9 Ethical considerations

- The mean effective dose of a chest X-ray examination in two views (pa, lat) is 0.08 mSv (Wachabauer and Röthlin 2017).
- The targeted mean effective radiation dose for one thoracic ultra-low-dose-CT (ULDCT) is approx. 0.2 mSv. This corresponds to approximately one month of natural background radiation in Austria. Compared to standard-dose CT examinations, ULDCT of the thorax causes about one-twentieth to one-fortieth of effective radiation dosage. Therefore, its dosage is much closer to a chest X-ray in two views than to a standard-dose CT, or even a low-dose CT examination.
- Even the cumulative dose of both examinations comes with a negligible radiation dose. Thus, no negative effects are to be expected.
- A delay in diagnosis can be ruled out since each examination is promptly evaluated – before the examination for the second imaging modality is performed.
- Since no contrast medium is applied, adverse effects or events – in this context – can be ruled out.

10 Recruitment

All patients who are assigned to receive a clinically indicated chest X-ray by the emergency department of Vienna General Hospital – regardless of indication – are offered participation in this trial. Thus, only clinically indicated cases may be included.

Patients who meet the eligibility criteria and provide informed consent become participants in this trial and receive an ultra-low-dose-CT examination of the thorax in addition to a chest X-ray.

11 Study duration

Based on a preliminary analysis of frequency, the anticipated total study duration, including analysis of all parameters, is one year.

12 Radiation dose

- Chest X-ray: The reference dose for a chest X-ray in two views is approx. 0.08 mSv (effective dosage) (Wachabauer and Röthlin 2017).
- Thorax-ULDCT: based on recent publications regarding imaging in emphysema and dyspnea, as well as on measurements with a thorax-CT test-phantom performed with the specific CT devices used for the study (Siemens Somatom Drive and Siemens Somatom Force), an effective dose of approx. 0.2 mSv (corresponding to DLP 12.5) appears to be optimal for ULDCT (lowest dose possible with sufficient image quality). This dose is below the effective dose of one month of natural background radiation, which is referenced as 0.23 mSv per month in Austria (2.8 mSv per year). (Bundesministerium für Arbeit, Soziales, Gesundheit und Konsumentenschutz 2018a; Bundesministerium für Arbeit, Soziales, Gesundheit und Konsumentenschutz 2018b; Ditto et al. 2013)

The thorax-CT test-phantom used is model RS-111 by "Radiology Support Devices", Long Beach, California, USA.

13 Radiological analysis

Rationale behind the study design:

Prospective:

For ethical, practical, and legal reasons, the emergency physician always needs an immediate consensus report on both methods written by a single specialist in radiology in order to make a final treatment decision. This would not be possible without a significant delay, if two radiologists had to create two separate reports. The frequency with which diagnoses and therapies by radiologists and emergency physicians differ between Arm 1 and Arm 2 will be measured.

Retrospective:

This will involve a multi-reader analysis by four radiologists in training and four specialists. All eight physicians will independently read and report all examinations by means of structured reporting. The reading time is not specified. Two groups with all 300 patients each will be created: In the 1st group, the chest X-ray examinations of Pts. 1-150 and the Ultra-Low-Dose-CT examinations of Pts. 150-300 will be available. In the 2nd group, this will be reversed. All patients will be fully anonymized and randomized. Two radiologists in training and two specialists will first read and report on group 1, the other four doctors will first read and report on group 2. Between the evaluations of group 1 and group 2 there will be at least one month to prevent a possible recognition of a case.

The gold standard will be built from all available patient data at the end of the study, including the results of all imaging procedures, follow-up examinations, physical medical examinations, laboratory and histopathological tests and further diagnostic procedures (concerns all available data, regardless of whether the patient is admitted as an inpatient).

The structured findings are then compared with the gold standard to determine the accuracy, sensitivity and specificity of both procedures.

Documentation:

- Waiting time for the ULDCT will be logged.
- Waiting time for the X-ray will be logged.

14 Statistical analysis plan

Power and sample size:

A total of 250 participants is targeted.

This is based on the following assumptions:

- Accuracy of a chest X-ray is 80%
- Accuracy of a ULDCT of the chest is 93%
- Dropout rate is 20% (one in five potential participants)

According to calculations using NQuery Advanced (version 8.3.0.0), 123 participants per arm (total of approx. 250 participants) will be required to reach a power of 85% in a one-sided test (alpha 2.5%). Due to the assumption of a dropout rate of 20% (approx. one in five potential participants), a sample size of 300 is required.

Cross tabulation and χ^2 -tests will be used to compare percentages (e.g., accuracy, sensitivity, ...). Diagnostic confidence will be compared by applying a Mann-Whitney U test.

15 Compensation

None.

Participants will not receive any compensation.

16 Study suspension

Since no negative effects on patients are expected, the trial will be suspended or stopped only if it becomes obvious that ultra-low-dose-CT examinations do not offer any benefit.

17 Data management and data protection

Only patients with clinical indications for chest X-rays will be included. During the active diagnostic phase, these patients will be diagnosed and treated in the usual clinical setting and documented using the RIS (Radiology Information System). Thus, in this part of the study, open data will be used.

The evaluation of prospective and retrospective data will be subject to complete anonymization and randomization and will not be un-blinded at any time thereafter. Anonymization is performed by the vb.net - RND function, local software, and complete deletion of all personal, public, and private DICOM tags in the header.

The data will remain at the Medical University of Vienna (MUW) and the Vienna General Hospital (AKH Vienna). Backup copies, which will remain in-house, will be made to protect the data.

18 Funding

Administration and analysis will be carried out by an employee funded for one year by Siemens Healthineers, Erlangen, Germany. No additional funds are available.

Bibliography

Anon 2014. *Radiation Emissions from Computed Tomography: A Review of the Risk of Cancer and Guidelines*. Ottawa (ON): Canadian Agency for Drugs and Technologies in Health.

Berrington de González, A., Mahesh, M., Kim, K.-P., et al. 2009. Projected cancer risks from computed tomographic scans performed in the United States in 2007. *Archives of Internal Medicine* 169(22), pp. 2071–2077.

Brenner, D.J. and Hall, E.J. 2007. Computed tomography--an increasing source of radiation exposure. *The New England Journal of Medicine* 357(22), pp. 2277–2284.

Bundesministerium für Arbeit, Soziales, Gesundheit und Konsumentenschutz 2018a.

Strahlenanwendung in der Medizin | Gesundheitsportal [Online]. Available at:

<https://www.gesundheit.gv.at/leben/umwelt/radiokativitaet/medizin> [Accessed: 22 November 2018].

Bundesministerium für Arbeit, Soziales, Gesundheit und Konsumentenschutz 2018b.

Strahlenbelastung in Österreich | Gesundheitsportal [Online]. Available at:

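### No pre-imaging record of the emergency physician's diagnosis or plan: the change outcomes capture only what the second modality adds, and first-line impact cannot be estimated

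*Combined protocol and SAP*

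**What the plan says.** Section 4 gives, as an aim beyond accuracy, to "analyze the clinical relevance of both methods by assessing the respective impact on final diagnosis", together with possible changes in therapy. It presents ULDCT as a possible primary imaging alternative to chest X-ray.

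Section 5 describes two records per patient, in a randomised order of reports:

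- **Plain film first (Arm 1, taking the arms in the order listed).** "Emergency physicians will first receive the report for the plain film of the chest and will be asked for the diagnosis and its probability". The ULDCT report follows, and then "Again, diagnosis and probabilities will be documented".
- **ULDCT first (Arm 2).** "Emergency physicians will first receive the report for the ULDC of the chest and will be asked for probabilities of the nine most frequent diagnoses", plus a category for other diagnoses. After the plain film report they "will again be asked to give an estimation of the probabilities for the same diagnoses as before".

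Section 6 lists as a secondary outcome "Frequency of change in emergency physician" diagnosis, and a matching one for the planned course of treatment. Section 13 (Prospective) says that the frequency with which physicians' diagnoses and therapies differ between the two arms will be measured. It does not say which of the two records is meant. Section 14 gives general tests for percentages and for confidence, and no analysis specific to the physician outcomes. No section describes a diagnosis, probability or treatment plan recorded before imaging.

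**The concern.** A change needs a before and an after. With two records per patient, both taken after a report, the only within-patient change available runs from the first report to the second. In Arm 1 that is what ULDCT adds to a known plain film; in Arm 2 it is what plain film adds to a known ULDCT. Neither is the effect of a method used as the first test, which is the use that Section 4 has in view.

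The results are easy to misread. Few changes in Arm 2 could be reported as plain film having little impact, when they show only that it adds little once ULDCT is known. Many changes in Arm 1 could be reported as the impact of ULDCT, when the plain film had already moved the diagnosis, rightly or wrongly. A pre-imaging judgement that was not written down at the time cannot be recovered later.

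**Working it through.** **1. What the records identify.**

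| Quantity | Records needed | Available? |
|---|---|---|
| Change caused by plain film as first test | before imaging; after first report, Arm 1 | No |
| Change caused by ULDCT as first test | before imaging; after first report, Arm 2 | No |
| ULDCT first v plain film first, state after one report | first records, Arm 1 v Arm 2 | Yes, by randomisation |
| Increment of the second method | first and second records, within arm | Yes |

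**2. The plan's own figure.** Section 14 gives accuracies of 80% and 93%, one-sided alpha 2.5%, power 85% and 123 per arm. For two independent proportions with pooled variance under the null:

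n = [z(0.975) × √(2 × 0.865 × 0.135) + z(0.85) × √(0.80 × 0.20 + 0.93 × 0.07)]² / 0.13² = (1.960 × 0.4833 + 1.036 × 0.4744)² / 0.0169 = 122.5, so 123 per arm.

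The figure reproduces. Its structure, two independent groups, is also that of a comparison of first records. If the physician's first diagnosis had these accuracies (an assumption; the plan gives them for the imaging methods), power would be 77% with 100 per arm, 84% with 120, 85% with 123 and 91% with 150.

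**3. What does not depend on the baseline.** Under the same assumption, let b be the proportion correct before imaging. The gain is 80 - b for plain film first and 93 - b for ULDCT first.

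| b (assumed) | Gain, plain film first | Gain, ULDCT first | Difference |
|---|---|---|---|
| 50% | 30 | 43 | 13 |
| 60% | 20 | 33 | 13 |
| 70% | 10 | 23 | 13 |
| 80% | 0 | 13 | 13 |

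Each method's own gain is unknown without b. The difference is 13 points throughout.

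**4. What does depend on it.** The listed outcome is frequency of change, not accuracy. Let L be the percentage of patients moved from right to wrong by the first report. The percentage moved from wrong to right is then gain + L, so the percentage whose status switches is gain + 2L. L cannot exceed the percentage wrong after the report: 20 for plain film, 7 for ULDCT. At b = 50%:

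- plain film first: 30 + 2L, from 30 to 70;
- ULDCT first: 43 + 2L, from 43 to 57;
- ULDCT minus plain film: from 43 - 70 = -27 to 57 - 30 = +27 points.

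The same limits follow at b = 60%, 70% and 80%, because b cancels. These are outer limits, not likely values. They show that first records fix the accuracy difference but not even the sign of the difference in change rates.

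**5. Precision from a pre-imaging score.** For a probability score with equal variances (set to 1) and correlation r between the pre-imaging and first-report scores (r is assumed; the plan gives none):

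- adjusted for the pre-imaging score: variance 1 - r², a saving of 25% at r = 0.5 and 49% at r = 0.7;
- unadjusted change score: variance 2(1 - r), a saving of 0% at r = 0.5 and 40% at r = 0.7.

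**The case against.** The strongest reply is that the question is comparative. Every participant already has a clinically indicated chest X-ray, so the contrast of interest is ULDCT against plain film, not imaging against none. Randomised order balances the unrecorded baseline, and Section 13 foresees a comparison between arms. Section 4 speaks of impact on the final diagnosis and does not define it as a change from a pre-test opinion. A raw change rate also counts changes to a wrong diagnosis, so it is not obviously the better target.

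Much of this stands. A reader might infer from Sections 5 and 6 that the trial can measure only what each method adds after the other. The documents do not support that: the first record follows plain film alone in one arm and ULDCT alone in the other, and comparing them is a valid randomised contrast.

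The reply does not settle the matter, for three reasons. The outcomes that Section 6 lists for physicians' diagnosis and therapy are change frequencies, which the first records alone cannot supply. Section 13 leaves open whether first records or change rates are compared. And Section 5 asks for a diagnosis with its probability in one arm and for a set of probabilities in the other, which weakens the comparison on which the reply depends. Planned therapy is less secure still: Section 5 does not say when it is recorded, and no reference standard for it is described.

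**Conclusion.** The point holds in a limited form. The absolute impact of either method as first imaging, on diagnosis or on planned therapy, cannot be estimated for any patient, and the change outcomes measure added value only. The relative contrast of first records is estimable without a baseline, but the plan neither names it nor collects it in the same way in both arms.

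The first conclusion rests only on the absence of any pre-imaging record in the documents. The 13-point and ±27-point figures assume that the planning accuracies carry over to the physician's first diagnosis. It would be wrong to expect a precision gain of 25% to 49% simply from analysing change: that range belongs to covariate adjustment, and it depends on the assumed correlation.

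This affects a stated secondary aim, not the primary accuracy hypothesis. It should be changed because the remedy is cheap and the missing information cannot be collected afterwards.

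**What to change.** **Section 5.** Use one identical form in both arms: probabilities for the nine diagnoses plus the category for others, and the planned course of action. The emergency physician completes it after consent and before any imaging report is released, and again after each report. State how the leading diagnosis is read from the probabilities.

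**Section 6.** Define three quantities:

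1. *First-line impact*: the change from the pre-imaging form to the form after the first report, compared Arm 1 v Arm 2.
2. *Comparative answer*: the Arm 1 v Arm 2 comparison of first records, adjusted for the pre-imaging score where the outcome is a probability.
3. *Added value*: the change from the first to the second report, kept as a separate outcome and labelled as such.

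**Sections 13 and 14.** Say which record the comparison between arms uses, and name the analysis for each quantity.

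**Cost.** A short amendment and one further form per patient, together with a common form for the records already planned. No extra imaging or patients are needed. The downsides are a little physician time at referral and possible anchoring on the first written opinion, which should be equal in both arms. If the extra form is refused, harmonise the two existing questions, name the comparison of first records as the answer to the aim in Section 4, and state that absolute first-line impact is not estimated.

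### The first primary component counts changed reports without limiting them to the primary diagnosis, so accidental findings seen only on CT can tilt it towards ULDCT

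*Combined protocol and SAP*

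**What the plan says.** Section 6 states the null as "There is no difference in accuracy between ULDCCT of the thorax and plain film of the thorax regarding the primary diagnosis". The alternative is limited to the primary diagnosis in the same way.

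The primary outcome in Section 6 has two components:

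- Initial accuracy is "assessed by analyzing the number of reports that are changed after the images of the second modality become available to the radiologist", Arm 1 against Arm 2.
- In a final step, "the diagnostic accuracy will be analyzed by retrospectively comparing all reports with the gold standard".

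The secondary outcomes in Section 6 include "Frequency of change in radiological diagnosis" and, separately, "Frequency of accidental diagnosis in ULDCT of the chest and plain film of the chest".

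Section 5 describes the second step. In Arm 1 (plain film, then ULDCT), "the findings of both examinations will be summarized, and a second report will be filed". In Arm 2 (ULDCT, then plain film), the radiologist has the option of adding a separate section to the report after seeing the film.

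No section defines a changed report, ties it to the primary diagnosis, or says how an added accidental finding is handled.

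**The concern.** The quantity counted is wider than the quantity in the hypotheses. The plan itself treats a change of diagnosis and an accidental diagnosis as outcomes of their own, so it expects accidental findings, yet nothing keeps them out of the primary count.

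The effect has a direction. In Arm 1 an accidental finding that only cross-sectional images show enters the second report. That report then differs from the first even if the primary diagnosis was right and stays the same. In Arm 2 the CT has already been read, so the film has less to add. Section 4 supports the direction: it says that superposition hides structures on projection images and that CT is free of it. The asymmetry would remain if both arms filed second reports under identical instructions.

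At stake is how a positive result is read. A higher yield of accidental findings could be presented as higher accuracy for the primary diagnosis, and the same findings would appear both in a primary and in a secondary outcome.

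**Working it through.** **Inputs from the documents (Section 14).** Accuracy 80% for plain film and 93% for ULDCT; one-sided alpha 2.5%; power 85%; 123 per arm; chi-square tests for percentages.

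**Inputs assumed.** The documents give neither the rate at which reports change nor the rate of accidental findings. Let c be the probability that the primary diagnosis changes at the second step (equal in both arms), and a1 and a2 the probabilities of an accidental-only addition in Arms 1 and 2, independent of c. The chi-square test is assumed to apply to this count.

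**Step 1: the plan's own figure.** Pooled normal approximation without continuity correction, mean proportion (0.80 + 0.93)/2 = 0.865:

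n = [1.960 × √(2 × 0.865 × 0.135) + 1.036 × √(0.80 × 0.20 + 0.93 × 0.07)]² / 0.13² = 122.5, rounded up to 123 per arm.

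This reproduces the stated 123 (power 85.1%). The calculation is for accuracies, not for change frequencies.

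**Step 2: probability of a changed report.** If any added finding counts, p = 1 − (1 − c)(1 − a). With c = 10% and a2 = 1%, Arm 2 has 1 − 0.90 × 0.99 = 10.9%. With a1 = 10%, Arm 1 has 1 − 0.90 × 0.90 = 19.0%.

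**Step 3: rejection rate.** Exact enumeration of two binomials, 123 per arm, pooled test, rejecting in favour of ULDCT when z > 1.96:

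| a1 (Arm 1) | Changed, Arm 1 v Arm 2 (c = 10%) | Rejection, c = 5% | c = 10% | c = 20% |
|---|---|---|---|---|
| 1% (equal to Arm 2) | 10.9% v 10.9% | 2.4% | 2.5% | 2.6% |
| 5% | 14.5% v 10.9% | 19.2% | 13.3% | 8.9% |
| 10% | 19.0% v 10.9% | 61.4% | 43.7% | 26.2% |
| 15% | 23.5% v 10.9% | 90.2% | 76.2% | 52.0% |
| 20% | 28.0% v 10.9% | 98.7% | 93.6% | 76.2% |

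The first row shows that the excess comes only from the difference between a1 and a2.

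**Step 4: other assumptions.** With no additions in Arm 2 and c = 7%, 13.5% or 20% (one minus the stated accuracies, and their midpoint), a1 = 2% gives 7.5%, 5.9% or 5.1%, and a1 = 10% gives 63.6%, 43.4% or 31.5%. With a2 = 2% and a1 = 10%, the rates are 42.4%, 29.1% and 21.5%.

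**Step 5: counting only the primary diagnosis.** The terms a1 and a2 drop out, and the rate returns to 2.4% to 2.6% for c = 7% to 20%, within this model.

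**Step 6: what the model leaves out.** It sets equal change rates, and equal accuracy does not imply them. Assume two equally accurate modalities that disagree in 20% of patients, with the radiologist siding with CT in 70% of those cases in either order. Primary-diagnosis changes are then 0.20 × 0.70 = 14% in Arm 1 and 0.20 × 0.30 = 6% in Arm 2. The same test rejects 56% of the time with no accidental findings at all.

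**The case against.** **The term is undefined, which is not the same as defined broadly.** A reader might infer that the plan has decided to count every change. It has not. In Arm 1 a second report is always filed, so an extreme literal reading would make nearly every Arm 1 report changed, and some criterion of content must be intended. The hypotheses stand just above, and the prospective part of Section 13 speaks of differences in diagnoses and therapies. This is fair, but it does not settle the matter: Section 13 does not restrict itself to the primary diagnosis, and an accidental finding is also a diagnosis. Nor would a separate secondary outcome for change in diagnosis be needed if the primary count already meant that.

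**No test is attached to this count.** A reader might infer that the trial's confirmatory test will reject a true null. The documents do not support that. Section 14 names chi-square tests for percentages in general, the sample size rests on accuracies, and the gold-standard component does not use the change count. This stands in full. What remains is that the count is listed first under the primary outcome, and no rule says which component decides.

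**The rates are assumed.** This also stands. Section 4 supports the direction of the tilt but not its size, and with equal accidental rates there is none.

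**The remedy is not sufficient.** Step 6 of the working bears this out: restricting the count to the primary diagnosis does not turn it into a test of equal accuracy.

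**Conclusion.** The point holds for the first primary component only. As worded, its count is wider than the hypotheses and takes in accidental additions. It is therefore tilted towards ULDCT whenever CT-only accidental findings are more frequent than film-only ones. The direction follows from the order of reading and the plan's own background; the size cannot be fixed from the documents. The 13% to 94% range is an illustration that rests on the assumed change and accidental rates, independence of the two, 123 per arm and the chi-square test. It is not an estimate of the trial's error rate.

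The gold-standard component is untouched, so the documents do not support a claim that the trial's conclusion on accuracy is invalid. The wording should be changed because the change is cheap and removes a bias of known direction.

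**What to change.** In Section 6:

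1. Define the first component as the number of reports in which the primary diagnosis differs between the first and the second report, judged by the same rule in both arms. Say how a primary diagnosis is told apart from an accidental one, and fix that rule before the reports are compared.
2. State that an accidental diagnosis added or removed while the primary diagnosis is unchanged does not count, and is reported only under the accidental-diagnosis outcome.
3. Keep the count of all changed reports as a descriptive secondary figure. State how it and the redefined count relate to the existing outcome "Frequency of change in radiological diagnosis", which would otherwise largely duplicate the redefined count.
4. State that the conclusion on accuracy rests on the gold-standard comparison, since a change count has no reference standard.

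The cost is a few sentences, a rule for primary against accidental diagnoses in a cohort enrolled whatever the indication, and a primary-diagnosis field in both reports. Fewer changes will be counted, and the apparent advantage of ULDCT on this component will be smaller. The stated 123 per arm, which was calculated for accuracy, does not change.
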